## **6.2. Demographics and baseline characteristics**

The following demographics and baseline characteristics will be presented in summary tables by treatment for the ITT and SAF (excluding ITT) populations: demographic characteristics (age, sex, race, ethnicity), weight, height, BMI, pulse, medical history, prior medications, laboratory examinations, vital signs, and ECG.

## **6.3. Patient disposition**

Patient disposition will include the number of patients who enroll in the study and the number and percentage of patients included in each analysis population. The frequency and percentage of patients who withdraw or discontinue from the study, along with the reason for withdrawal or discontinuation, will be summarized by treatment.

## 7. Primary efficacy analyses

The efficacy analysis will be conducted within the estimand framework. A summary of the attributes of the estimand is provided in Table 1.

**Table 1. Estimand attributes for the primary efficacy analyses**

Estimand attribute	Description
Population	Full analysis set population, which consists of all patients who receive at least one dose of study drug and have baseline average pain intensity score and at least one post-baseline average pain intensity score.
Endpoint	Change from baseline in weekly mean of daily average pain based on the 11-point NRS at 12 weeks.
Intercurrent events	All values collected after treatment discontinuation will be included in the analysis. All missing values due to treatment or study discontinuation will be imputed using reference-based imputation with missing values imputed based on the placebo data. All other intermittent missing values will be imputed under the assumption of missing at random with each missing value imputed based on the treatment group assignment. Any missing values related to software issues with the electronic diary will be treated as missing at random. This hypothetical scenario assumes that the treatment had no further benefit in patients that discontinued study medication while accounting for the disease trajectory and trial effect.
Summary measure	Difference between ricolinostat arm and placebo arm as measured by change from baseline in average pain at Week 12.

The primary estimand is the difference in the mean change from baseline through Week 12 in the average pain score as measured by the NRS. The null and alternative hypotheses to be tested for these estimands are  $H_{01}: \Delta_{RIC} = \Delta_{PBO}$  and  $H_{A1}: \Delta_{RIC} \neq \Delta_{PBO}$  where  $\Delta_{RIC}$  denotes the average change from baseline in the average NRS score at Week 12 in the ricolinostat arm, and

$\Delta_{PBO}$  for the placebo arm. The hypothesis will be tested using a mixed model repeated measures (MMRM) model as described Section 7.2.

### **7.1. Primary analysis**

The primary analysis will use a mixed model repeated measure (MMRM) approach with all missing values imputed using the method of reference-based multiple imputation. Using this approach, missing values resulting from treatment and/or study discontinuation are imputed using the information in the placebo group. Reference-based imputation assumes that any missing data are not missing at random. Intermittent missing values will be imputed assuming MAR with imputed values estimated based on the patient's treatment group assignment. The model and details of the imputation approach are discussed further in this section. The strategy for the analyses is as follows:

1. Fit the MMRM using an unstructured covariance matrix. If the model fails to converge, additional covariance structures will be tested until a covariance structure is identified. Once the covariance structure is identified, the structure will be used for all modeling. (See Section 7.2)
2. Using MAR multiple imputation, intermittent values will be imputed based on the treatment group to which the patient is randomized. (See Section 7.3)
3. Apply reference-based multiple imputation to the data sets obtained from the MAR multiple imputation and obtain the results for the primary efficacy analysis. (See Section 7.3)
4. Conduct the appropriate sensitivity analyses. (See Section 7.4)

### **7.2. Identification of the primary model**

The primary endpoint is change from baseline in mean average pain intensity over the 12 weeks of treatment as measured by the weekly average NRS in the FAS population. The primary endpoint will be analyzed using a MMRM analysis. The MMRM will be fit with the weekly mean change from baseline in the NRS score at Weeks 1, 2, 4, 8 and 12 as the outcome. The following covariates will be included in the model: baseline NRS score, visit, treatment group, concomitant medication for painful DPN (yes vs. no), treatment group by visit interaction term, and baseline NRS score by visit interaction. A restricted maximum likelihood will be used as the method of estimation with the degrees of freedom approximated using the

Kenward Rogers approach (see Table 4 for an example of the MMRM code to be used for the primary model). The model will be fit with an unstructured covariance matrix. If the MMRM with an unstructured covariance matrix does not converge, the following covariance structures will be substituted in the order listed below. Each subsequent covariance structure will be used only if each previous covariance structure fails to converge. The covariance structure for the final model will be the first structure in the sequence that produces a stable model that converges.

1. Toeplitz covariance structure (assuming measurements taken closer together in time are more highly correlated than those taken farther apart).
2. First order auto-regressive (AR[1]) covariance structure (assuming measurements taken closer together in time are more highly correlated than those taken farther apart, but more constrained than the Toeplitz structure).
3. Compound symmetry covariance structure (assuming equal correlation for measurements from a patient, regardless of how far apart in time when they were taken).

Once the primary model is established, this model will be used for all analyses.

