Statistical Methods:	
Primary Analysis
 
The primary analysis will be based on a mixed model repeated measures (MMRM) analysis to estimate the difference in change from baseline to Week 12 in mean average pain score in patients receiving ricolinostat versus those receiving placebo. The outcome will include the weekly mean change from baseline in the daily average pain scores computed each week during Week 1 through Week 12. The baseline average pain score will be computed as the mean of the average daily pain scores during the 7 days prior to randomization. The following covariates will be included in the model: baseline value of the pain score, visit, treatment group, use of concomitant medication for painful DPN (yes vs. no), a treatment group by visit interaction term, and a baseline pain score by visit interaction term. The model will first

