## **10.3 Statistical Methods**

### **10.3.1 Sample Size and Power**

The sample size for this study is planned to be approximately 274 evaluable patients, which provides a power of 0.8 for detecting a treatment difference of 0.8 points on the NRS. Assuming a pooled standard deviation of 2.35, this corresponds to a standardized effect size of approximately 0.34, an effect size comparable to effect sizes observed in recent diabetic neuropathic pain studies using efficacious agents such as duloxetine and pregabalin (Smith et al, *Journal of Pain*, 2018). An effect size of this magnitude or greater, if observed in this study, would support the further investigation of ricolinostat as a potential treatment for painful DPN. The estimates for power are conservative as the primary efficacy analysis will use an MMRM approach with 12 measures over time.

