A MMRM approach will be used to analyze the change from baseline to Week 12 in the average NRS pain score, with the mean change from baseline in the average NRS pain score at each week as the outcome in the model. The model will include the following covariates: treatment, visit, treatment by visit interaction, baseline NRS pain score, baseline NRS pain score by visit interaction, and use of concomitant medication for painful DPN (yes vs. no). The within-patient correlation will be modeled by using an unstructured covariance matrix. If the model does not converge, then a Toeplitz covariance structure will be used, which assumes that observations closer together are more correlated than those further apart in time. If convergence

is still not attained, then the auto-regressive of order one will be used, which has the same assumption as the Toeplitz model but is more restrictive. If the model still does not attain convergence, then compound symmetry variance-covariance models will be used, which assume equal correlation between measurements from a patient. Restricted maximum likelihood will be used as the method of estimation with the degrees of freedom approximated using the Kenward Rogers approach. The primary estimand will be obtained from this model.

It is assumed that short-term action of rescue medication does not affect the average daily pain score and scores that are collected during the use of rescue medication will be used in the analysis. Patients on a stable dose of permitted concomitant medication that has been started at least 3 months prior to starting the Pain Observation period will be included in the analysis. However, if there is a dose change, the pain scores after dose change will be set to missing and imputed under the assumption of MAR.

In order to assess the robustness of the primary analysis, the following additional sensitivity analyses will be performed:

1. A tipping point analysis with multiple imputation, in which the missing values in the ricolinostat arm will be assigned a shift parameter during imputation in order to determine the point where statistical significance changes.
2. An MMRM analysis with jump to reference, in which all missing values are imputed based on the placebo arm. This is a worst-case scenario where missing values among patients in the ricolinostat arm are imputed as if they came from the placebo arm.
3. An MMRM analysis using MAR and monotone missing assumptions.

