#### 7.4. Sensitivity analyses

The following sensitivity analyses will be performed:

1. MMRM based on the data as observed, noting that incomplete diary data for a given week is defined as missing (see Section 6.1.5.1). A MMRM will be fit to the data using all non-missing values. This analysis will use a modification of the code presented in Table 4.
2. A MMRM model will be fit using missing at random imputation. Using this approach all missing values will be imputed based on the treatment group to which the patient was randomized.
3. A tipping point analysis will be conducted to assess the robustness of the result and the validity of the missing at random assumption.

The code for the use of missing at random multiple imputation is provided below. The input dataset to execute this code is OUT\_IMP\_CONT which is obtained from running the code provided in Table 2. After running the code in Table 6, the code provided in Table 4 and Table 5 is executed with the dataset names changed as needed.

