## 9. Secondary analyses

The secondary endpoints for this study and a description of the analysis approach for each endpoint are provided below:

- Change in weekly mean worst pain from baseline to Week 12 and Week 4 as measured by the NRS will be analyzed using MMRM as outlined in Section 7.2.
- Proportion of patients achieving  $\geq 30\%$  and  $\geq 50\%$  improvement in mean NRS score from baseline to Week 4 and to Week 12 – will be summarized descriptively. Comparisons between the ricolinostat and placebo groups will be made using a Fisher's exact test.
- Change in mean BPI-SF pain interference score from Pre-Treatment/Day 1 to Week 12 will be analyzed using MMRM as outlined in Section 7.2.
- Change in mean BPI-SF pain interference score from Pre-Treatment/Day 1 to Week 4 will be analyzed using MMRM as outlined in Section 7.2.
- Change from baseline to Week 12 in the NTSS-6 will be analyzed using MMRM as outlined in Section 7.2.
- Change from baseline to Week 12 in Norfolk diabetic QOL-DN score will be analyzed using MMRM as outlined in Section 7.2.
- PGIC at Week 4 and Week 12 will be analyzed using an ANCOVA model with treatment group as a covariate.
- Rescue medication (acetaminophen) use will be analyzed based on mean daily used from baseline to Week 12 and mean weekly used from baseline to Week 12. Mean weekly use from baseline to Week 12 will be analyzed using the MMRM approach outlined for the primary efficacy analysis.

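### SAP 7.2 models five of the protocol's twelve weekly pain means; without imputation, some early leavers then lose their last score, which gives a modest bias mainly if pain-driven dropout differs by arm

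*SAP*

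**What the plan says.** **Protocol.** The synopsis defines the outcome as the "weekly mean change from baseline in the daily average pain scores computed each week during Week 1 through Week 12". Section 10.3.3 fits the MMRM "with the mean change from baseline in the average NRS pain score at each week as the outcome in the model". Section 10.3.1 calls the power conservative because "the primary efficacy analysis will use an MMRM approach with 12 measures over time".

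**SAP.** Section 7.2 fits the MMRM with the "weekly mean change from baseline in the NRS score at Weeks 1, 2, 4, 8 and 12 as the outcome" and adds: "Once the primary model is established, this model will be used for all analyses". The Table 4 contrast has ten treatment-by-visit coefficients, five per arm. Section 1 makes the SAP govern where the two documents differ on planned analyses. No reason is given for leaving out Weeks 3, 5-7 and 9-11, although the diary is completed daily.

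The SAP's imputation code (Tables 2, 3, 6 and 7) names the changes at all twelve weeks, and no step is described that reduces twelve to five.

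Two diary-pain analyses have no imputation:
- **As-observed sensitivity analysis (7.4 item 1):** "A MMRM will be fit to the data using all non-missing values", by a modification of the Table 4 code.
- **Worst pain (section 9):** "Change in weekly mean worst pain from baseline to Week 12 and Week 4 as measured by the NRS will be analyzed using MMRM" as set out in 7.2. Section 6.1.5.3 says missing secondary data are not imputed and that these endpoints are analysed on complete cases.

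**The concern.** A likelihood-based MMRM is valid under missing at random given the data that are in the model. If patients leave because of recent pain, the score just before dropout is what makes that assumption credible. On the five-visit grid, a patient who leaves after Week 11 contributes nothing after Week 8.

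At stake is how the sensitivity analyses are read. Items 1 and 2 of SAP 7.4 both rest on missing at random, but item 2 imputes from twelve weeks while item 1, if it follows 7.2, conditions on five. A gap between them could come partly from the omitted weeks and be taken for sensitivity to missing-data assumptions.

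**Working it through.** **1. The plan's own figure.** Inputs (protocol 10.3.1 and 10.3.3, SAP 6.1.1): difference 0.8, SD 2.35, two-sided 0.05, power 0.80, 1:1 allocation.
- Effect size: 0.8 / 2.35 = 0.340.
- n per arm = 2 × (1.960 + 0.842)² / 0.340² ≈ 136, or 272 in total. With 137 per arm the t-test has power 0.802. The planned 274 reproduces and is not in dispute.
- Complete-data standard error: 2.35 × √(2/137) = 0.28.

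**2. Who loses a score.** An early leaver's last observed week can be any of 1 to 11. Weeks 1, 2, 4 and 8 are on the SAP grid. The other seven (3, 5, 6, 7, 9, 10, 11) are not. In the simulations below, 42-59% of early leavers had their last week off the grid.

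**3. Simulated bias in a non-imputed MMRM.** The documents give no dropout rate and no week-to-week correlation, so these are assumed:
- SD 2.35 at every week; correlation a + (1 − a) r^lag with (a, r) = (0, 0.9), (0.5, 0.8) or (0.6, 0.6).
- Dropout of 15% or 25% by Week 12, with log-odds of leaving of 0.5 or 1.0 per NRS point of the latest weekly score. The data are therefore missing at random given all twelve weeks.
- Maximum likelihood for monotone data, 150,000 patients per arm, fitted to twelve weeks and to the five SAP weeks.

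Examples with (a, r) = (0.5, 0.8). Bias is in NRS points; the difference is ricolinostat minus placebo, so a positive bias goes against ricolinostat.

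| True effect | Target dropout, slope | Pain drives dropout in | 12-week bias, difference | 5-week bias, placebo / ricolinostat | 5-week bias, difference |
|---|---|---|---|---|---|
| 0.8 | 15%, 0.5 | placebo only | +0.001 | −0.038 / +0.003 | +0.042 |
| 0.8 | 25%, 1.0 | placebo only | +0.007 | −0.110 / +0.002 | +0.112 |
| 0.8 | 15%, 0.5 | both arms | +0.005 | −0.046 / −0.030 | +0.016 |
| 0.8 | 25%, 1.0 | both arms | −0.007 | −0.112 / −0.078 | +0.034 |
| 0 | 25%, 1.0 | both arms | 0.000 | −0.121 / −0.122 | −0.001 |

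Over all scenarios in this set, the twelve-week model is within 0.007 of the truth. The five-week difference is off by 0.04 to 0.14 when pain drives dropout in one arm. With the same mechanism in both arms it is off by 0.01 to 0.05 if the effect is 0.8, and by about 0 if there is no effect.

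**4. Other assumptions.**
- 3,000 trials per scenario, 137 per arm, SD rising from 1.5 to 2.35, dropout 14-24%. With stronger dependence on placebo, the five-visit estimate is −0.73 to −0.77 against a true −0.8 (bias 0.04-0.07 as computed before rounding), and the twelve-week estimate is −0.79 to −0.81. With equal dependence the bias is under 0.01. Standard errors are essentially the same. About 10-12% of all patients have observed weekly means after their last modelled visit.
- 20% dropout, slope 0.5: bias of 0.02-0.08 in either direction when the mechanism differs by arm, under 0.01 when it is the same.

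**5. Scale.** 0.02 to 0.14 is 0.02/0.8 = 2.5% to 0.14/0.8 = 17.5% of the planned effect, and 0.02/0.28 = 0.07 to 0.14/0.28 = 0.5 of a standard error.

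**The case against.** **The analyses that decide the trial are hardly touched.** This stands. The primary, missing-at-random imputation and tipping-point analyses impute from all twelve weeks. A reader might infer that the primary estimate is biased or that power is lost. The documents do not support either: the off-grid scores enter at the imputation step, the sample size reproduces, and the simulated standard errors barely differ. What remains is one sensitivity analysis and one secondary endpoint outside the fixed testing sequence.

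**SAP 7.4 item 1 may already mean twelve weeks.** Its reference to all non-missing values, and to modified Table 4 code, allows that reading. The rule in 7.2 that one model serves every analysis, and the five-visit contrast, point the other way. So discarded data are the likelier reading but not a certain one.

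**The complete-case rule pre-empts the worst-pain argument.** This stands too. Read literally, SAP 6.1.5.3 removes early leavers altogether, and adding weeks would recover nothing. If it means that every modelled week must be present, twelve weeks would exclude more patients than five.

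**Five visits may be deliberate.** They are the scheduled double-blind visits, and an unstructured matrix needs 5 × 6 / 2 = 15 parameters against 12 × 13 / 2 = 78. That is a defensible trade-off, but the SAP does not state it, and a fallback order handles it.

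**Items 1 and 2 need not agree exactly anyway.** Correct. The imputation runs by arm and rounds to 0.1, while the MMRM pools covariance across arms. A gap would not by itself show that the visit grid is the cause.

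**Conclusion.** The conflict between the documents is real, and so is the mismatch inside the SAP between twelve imputed weeks and five modelled weeks. The consequence is modest and conditional. If the as-observed MMRM follows 7.2, the Week 12 difference can be off by roughly 0.02 to 0.14 points when pain-driven dropout differs by arm, and by about 0 to 0.05 when it does not. Pain-driven dropout on placebo alone biases against ricolinostat; the reverse pattern would favour it. These sizes rest on assumed dropout rates, slopes and correlations.

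Two broader readings go too far. Not all early leavers lose their last score: those who leave after Weeks 1, 2, 4 or 8 keep it. Nor does pain-driven dropout alone bias the treatment difference appreciably, because the arm-level biases largely cancel when the mechanism is shared. For worst pain the point holds only if all available weekly means are analysed. This is a worthwhile correction, not a threat to the primary conclusion.

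**What to change.** 1. In SAP 7.2, Table 4 and 7.4 item 1, make the outcome the weekly mean change at all of Weeks 1-12, with a twelve-visit contrast.
2. If the twelve-visit unstructured covariance does not converge, fall back to the five-visit unstructured model, and only then to the simpler structures listed in 7.2.
3. For worst pain, first replace the complete-case wording in 6.1.5.3 with use of all available weekly means, then apply the same twelve-week MMRM.

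The cost is SAP wording and code. The diary data are already collected, SAP 7.3.1 says its code is not final, and 5.1 leaves methods to be finalised at the blinded review. The downside is a somewhat higher risk of non-convergence with 78 rather than 15 covariance parameters, which step 2 covers. A final week with fewer than four diary entries is still set to missing on either grid.

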### 7.3. Primary efficacy analysis

The primary model, as outlined in Section 7.2, will be used for this analysis. The analysis will consist of three steps: identify the primary model and covariance structure, impute all intermittent missing values under the assumption of MAR, and impute all remaining missing values under reference-based imputation. After the imputed datasets are created, Rubin's rule is used to obtain the final estimates and significance levels.

#### 7.3.1. *Imputation of intermittent missing values*

The imputation of the intermittent missing values is executed using the code below. Note that the code presented here is not final and will be vetted on blinded data prior to use for the final analyses. The variables to be included in the analyses are as follows:

- DELT\_NRS – change from baseline in NRS. Note that DELT\_NRSX denotes the change from baseline in NRS at Week X.
- BASE\_NRS – baseline value of NRS

- AVISITN – denotes visit number
- CONMED – a yes/no variable indicating use of concomitant pain medication
- TRT – denotes treatment group
- USUBJID – denotes patient ID

---

**Table 2. SAS code to create datasets satisfying monotone missing condition**

---

```

** Rearrange data for use in PROC MI;
proc sort data= DATA_IMP(observed data set);
    by USUBJID TRT BASE_NRS;
run;

proc transpose data= DATA_IMP out=DATA_IMP1;
    by USUBJID TRT BASE_NRS;
    ID AVISITN;
    VAR DELT_NRS;
run;

proc sort data= DATA_IMP1;
    by USUBJID;
run;

proc mi data=DATA_IMP1 nimpute=100 round=0.1 seed=
out=OUT_IMP_TRT_RIN;
    where TRT eq "RIN";
    var    BASE_NRS(baseline) CONMED
           DELT_NRS1 DELT_NRS2 DELT_NRS3 DELT_NRS4
           DELT_NRS5 DELT_NRS6 DELT_NRS7 DELT_NRS8
           DELT_NRS9 DELT_NRS10 DELT_NRS11 DELT_NRS12;
    mcmc  chain=multiple impute=monotone;
run;

proc mi data=DATA_IMP1 nimpute=100 round=0.1 seed=
out=OUT_IMP_TRT_PBO;
    where TRT eq "PBO";
    var    BASE_NRS(baseline) CONMED
           DELT_NRS1 DELT_NRS2 DELT_NRS3 DELT_NRS4
           DELT_NRS5 DELT_NRS6 DELT_NRS7 DELT_NRS8
           DELT_NRS9 DELT_NRS10 DELT_NRS11 DELT_NRS12;
    mcmc  chain=multiple impute=monotone;
run;

data OUT_IMP_CONT;
    set OUT_IMP_TRT_RIN OUT_IMP_TRT_PBO;
run;

```

---

